1.0 Background

Patients undergoing hip arthroscopy experience moderate to severe postoperative pain. Effective pain control after surgery is an important component in the overall management of these patients. Good pain control encourages early participation in rehabilitation program, increases success of the surgery, and improves patient satisfaction. Typically, postoperative analgesia is provided to these patients either with nerve blocks (psoas compartment lumbar plexus block and sciatic nerve block) or opioid medications (1,2,3). Both these methods provide good pain relief but nerve blocks are associated with weakness of lower extremity muscles which interferes with early ambulation and increase the risk of falls while narcotic medications increase the risk of nausea, vomiting, itching, constipation, ileus, urinary retention, sedation and respiratory depression.

Liposomal bupivacaine has the same active ingredients as bupivacaine. Both act to block the generation and conduction of nerve impulses associated with pain. Liposomal bupivacaine consists of bupivacaine encapsulated within a hydrophobic lipid membrane. Bupivacaine is released from the multivesicular liposomes over a prolonged period of time. (4)

- Lumber Plexus Blockade Reduces Pain After Hip Arthroscopy: A Prospective Randomized Controlled Trial. YaDeau J, Tedore T, Goytizolo E, Kim D, Green D, Westrick A, Fan R, Rade M, Ranawat A, Coleman S, Kelly B. Anesthesiology & Analgesia 2012; 115(4): 968-972.
- 2. The analgesic impact of preoperative lumbar plexus blocks for hip arthroscopy. A retrospective review. Schroeder K, Donnelly M, Anderson B, Ford M, Keene J. Hip International 2013; 23(1): 93-8.
- 3. Are Femoral Nerve Blocks Effective for Early Postoperative Pain Management After Hip Arthroscopy? Ward J, Albert D, Altman R, Goldstein R, Cuff G, Yourn T. Arthroscopy: The Journal of Arthroscopic and Related Surgery 2012; 28(8): 1064-69.
- 4. Liposomal bupivacaine: A long-acting anesthetic for postsurgical analgesia. Formulary 2012.

2.0 Rationale and Specific Aims

Ultrasound guided peri-articular Hip infiltration with local anesthetic solution is an alternative analgesic technique that has been shown to reduce pain, opioid consumption and facilitate earlier discharge from hospital after surgery without causing any weakness of lower extremity. The typical duration of analgesia after peri-articular analgesia lasts only for 8-10 hours. When the effect of injected local anesthetic solution wears off, patients start relying on opioid pain medications for pain control. By using long acting liposomal bupivacaine for LIA we hypothesized that we will provide prolonged duration of analgesia and significantly reduce pain tablet consumption.

3.0 Inclusion/Exclusion Criteria

Inclusion Criteria:

- 1. Patients having hip arthroscopy
- 2. Patients between the ages of 18-80 years

Exclusion Criteria

- 1. History of neurologic disease, neuropathy, diabetes
- 2. Allergy to local anesthetic solution
- 3. Chronic use of narcotics
- 4. History of previous hip arthroscopy on the ipsilateral side
- 5. Pregnancy

4.0 Enrollment

Subjects will be consented in a private area prior to surgery. An investigator will explain the study and answer all questions.

5.0 Study Procedures

1. Preoperative evaluation and consent

2. General anesthesia for hip arthroscopy

3. Ultrasound guided injection of liposomal bupivacaine (experimental group) or bupivacaine (control group) (around the anterior, lateral and medial aspect of hip joint.

4. Hip arthroscopy

5. Postoperative recovery – assessment of pain and narcotic consumption using pain scores and 14-question survey

6. Discharge of patients from hospital to home

7. Patient records pain scores and completes 14-question survey

8. Follow up by telephone 24 hours and 96 hours after surgery to collect data

6.0 Reporting of Adverse Events or Unanticipated Problems Involving Risk to Participants or Others

If there are adverse events or unanticipated problems involving risk to the participants or others, they will be reported to the IRB within five working days after their occurrence.

7.0 Study Withdrawal/ Discontinuation

If the participant requests to be withdrawn from the study, the investigator will inform participant that their standard of care will remain the same and that there are no adverse indications from withdrawing. Their withdrawal statement will be added to the participant's Consent Form. The corresponding Study Subject Number will be removed from the study list. Discontinued participant records will not be used to compile the final report.

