9.0 Privacy/ Confidentiality Issues

Patients will be assigned a study subject number that will be used on all data collection documents. Their personal information (Name, address, telephone number, age, weight, height, sex, etc.) will only be recorded on one list with study subject numbers. This list will be separate from all other documents under lock and key and only used to make follow up phone calls. Study records are kept confidential. If the results of the study are published in a scientific journal or presented at a scientific meeting, the subjects' names and any identifiers will not be used.

[figure not shown]

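### Section 7.0 strikes a withdrawn patient's number from the study list and drops their records from the report even after the injection, with no provision for the code link, the remaining calls or recorded adverse events

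*Combined protocol and SAP*

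**What the plan says.** Section 7.0 of the protocol sets out what follows a request to withdraw. The withdrawal is documented on paper ("Their withdrawal statement will be added to the participant's Consent Form"), the code is taken off ("The corresponding Study Subject Number will be removed from the study list"), and the data are left out ("Discontinued participant records will not be used to compile the final report"). None of these steps depends on whether the injection has been given.

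Section 9.0, repeated in item 10.0 of the IRB application, explains the coding. "Patients will be assigned a study subject number that will be used on all data collection documents". Name, telephone number and other personal details "will only be recorded on one list with study subject numbers", and of that list it says: "This list will be separate from all other documents under lock and key and only used to make follow up phone calls".

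Section 5.0 puts the injection before the arthroscopy, and item 5.5 of the application lists it as a single administration. After discharge the only scheduled contacts are these: "Follow up by telephone 24 hours and 96 hours after surgery to collect data". Section 6.0 requires adverse events to be reported to the IRB within five working days and makes no exception for withdrawn patients.

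The IRB application adds two relevant statements. Item 9.1 answers yes to the consent form being the only record that links the subject to the study. Item 10.2 files the consent form and the data collection form in the research record.

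**The concern.** The treatment is one injection. A patient who withdraws afterwards has been exposed and remains so, and for the liposomal arm the lay summary in Section 4 of the application gives possible pain relief of up to 72 hours. A rule suited to someone who leaves before treatment is therefore also applied to treated patients.

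Two things are at stake. The first is the link: data forms carry only the number, so taking the number off the one described key leaves no documented way to match a form to a person. The second is the safety comparison. If records of treated patients are left out of the report, so are the adverse events in them, and the count by arm is then made on a subset selected after treatment. A patient may withdraw because of a reaction or poor pain control. The documents do not say how often that happens, but the rule would remove exactly those cases.

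**Working it through.** No figure in the plan belongs to this point, so the check is mainly a comparison of sections.

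**1. Which list is meant.** Section 7.0 speaks of the study list. Section 9.0 describes one list holding subject numbers with identifiers. No other list of subject numbers is described. That they are the same is a reasonable inference, not a statement.

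**2. What is removed.** Section 7.0 removes the number. It does not say that name or telephone number is deleted.
- *Link:* if the lists are the same, the pairing of number and person is gone from the only place where Section 9.0 keeps it.
- *Calls:* Section 9.0 says the list is "only used to make follow up phone calls", so removal from it implies that the calls end. This is not written.

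**3. How many contacts are affected.** Calls are scheduled at 24 h and 96 h.

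| Time of withdrawal after surgery | Scheduled calls still to come |
|---|---|
| before 24 h | 2 of 2 |
| 24 h to 96 h | 1 of 2 |
| after 96 h | 0 of 2 |

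Against the 72 h of possible pain relief in the lay summary, the 24 h call falls inside the period and the 96 h call falls 96 − 72 = 24 h after it.

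**4. What leaves the report.** Section 7.0 excludes discontinued participants' records without exception for adverse events. Section 6.0 still sends those events to the IRB. So an event can be reported to the IRB and yet be absent from the final report.

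**5. Which record holds the link.** Section 9.0: one list, kept apart from all other documents. Application item 9.1: the consent form, and only that. Both cannot be right. Neither says that the consent form carries the subject number.

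**6. Size.** Planned sample 36, 18 per group (application item 4.7); dropout 10% (Section 8.0).
- Patients: 0.10 × 36 = 3.6, so 3-4 in all; per group 0.10 × 18 = 1.8, so about 2.
- This is a ceiling. It assumes that every dropout is a withdrawal by request and occurs after the injection. The lower end is 0.
- Weight of one patient: 1/18 = 5.6% of a group. Leaving out one withdrawn patient with an event changes the group's figure from 1 of 18 (5.6%) to 0 of 17 (0%), if that was the only event.

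**The case against.** The best case against is that ending research contact is what withdrawal ordinarily means, that Section 7.0 leaves standard care unchanged, and that the duty to report to the IRB continues. That is fair, and it is why permission has to be sought for any further call. It does not justify leaving out adverse events recorded before the patient withdrew.

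Several stronger readings are tempting and not supported:

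- *Events can no longer be traced.* A reader might infer this from the single list. But the withdrawal statement goes on the consent form, the consent and data forms are filed in the research record (application item 10.2), medical records are a data source (item 7.5), and nothing is said to be destroyed. What is lost is the documented code link. Since no section says that the consent form bears the number, full traceability is not shown either.
- *The two calls are safety contacts.* Section 5.0 says they are made to collect data. They would pick up nausea, vomiting and constipation, which are secondary outcomes, and they are the only scheduled route by which an event at home would be learned of. The documents do not call them safety surveillance.
- *A letter about significant findings (Section 11 of the application) could not reach the patient, or an IRB report would lack the arm.* The address is not said to be deleted, and the list is not said to hold the arm.
- *The rest of the 72 h is a period of risk.* The documents give 72 h as possible pain relief, not as a risk window.

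The consent pages are not in the copy reviewed, so they may already cover contact or data retention after withdrawal.

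**Conclusion.** The point holds in a limited form. As written, Section 7.0 directs removal of the number and exclusion of the records of a patient who has already been injected. This is an explicit rule rather than an omission. The loss of adverse events from the report by arm follows directly from the text. The loss of the documented link and the end of the remaining calls depend on the study list being the list in Section 9.0; the end of the calls is implied only. The conflict between Section 9.0 and application item 9.1 stands regardless.

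At most 3-4 of 36 patients are affected, under the assumption that all dropout is by request and after injection. The number is small, but with 18 per group a single omitted event is 5.6% of a group. The change is cheap and should be made.

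**What to change.** In Section 7.0, separate withdrawal before the injection from withdrawal after it. Suggested text for the second case:

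> If the injection has been given, the subject number and its link to the participant are kept until follow-up is complete. The participant is asked whether the remaining 24 h and 96 h calls may still be made. Adverse events up to withdrawal, and later ones learned of with the participant's permission, are reported under Section 6.0 and tabulated by arm.

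Removing the number can remain the rule for those who withdraw before injection.

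The sentence "Discontinued participant records will not be used to compile the final report" must be amended together with this so that it does not exclude these adverse events; otherwise Section 7.0 would contradict itself.

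Reconcile Sections 5.0, 6.0, 7.0 and 9.0 with items 9.1, 10.0 and 10.2 of the IRB application: state which record holds the link, whether the study list is the list in Section 9.0, and whether the consent form carries the subject number.

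Cost: a wording change, a check that the consent form says the same, and one extra question to a withdrawing patient, who may refuse. Sample size, treatment and the efficacy analysis are unaffected.

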8.0 Statistical Considerations

S 5

Continuous data will be analyzed using parametric methods for normal distribution and non-parametric methods for non-normal distribution (Student t-test or Mann Whitney/Wilcoxon Sum test). Chi-squared or Fisher's exact tests will be used to analyze categorical data. Statistical significance will be set at $\alpha < 0.05$

Sample size of 36 was calculated based on our assumption that a mean difference of 1.0mg (± 1 SD) in intravenous hydromorphone administration in the recovery room between the experimental group and control group with a power of 80 % and $\alpha = 0.05$ (2 sided test) and a 10% dropout. Included is the power analysis:

```
t tests - Means: Difference between two independent means (two groups) Analysis: A priori: Compute required sample size Input: Tail(s) = Two Effect size d = 1.0  
\alpha err prob = 0.05  
Power (1-\beta err prob) = 0.80  
Allocation ratio N2/N1 = 1  

[figure not shown]
Output: Noncentrality parameter \delta = 2.9154759  
Critical t = 2.0369333  
Df = 32  
Sample size group 1 = 17  
Sample size group 2 = 17  
Total sample size = 34  
Actual power = 0.8070367
```

9.0 Privacy/ Confidentiality Issues

Patients will be assigned a study subject number that will be used on all data collection documents. Their personal information (Name, address, telephone number, age, weight, height, sex, etc.) will only be recorded on one list with study subject numbers. This list will be separate from all other documents under lock and key and only used to make follow up phone calls. Study records are kept confidential. If the results of the study are published in a scientific journal or presented at a scientific meeting, the subjects' names and any identifiers will not be used.

[figure not shown]
10.0 Follow-up and Record Retention

The duration of the study will last 96 hours after the participant's total knee replacement. Study records will be stored for three years after the close of the study. Study records will then be destroyed using the standard Saint Francis shredding service.

SAINT FRANCIS HOSPTIAL AND MEDICAL CENTE

Institutional Review Board
Full Board Application for Initial Project Approval

All applications must be typed. Point, click and type in the appropriate cell; cells will expand to accommodate text. Tabbing out of the last cell on the right of a table will insert another row. Referencing the protocol is not acceptable since not all IRB members receive the complete protocol. The IRB reserves the right to return applications that do not provide sufficient responses.

There are consent form templates available for the following study categories, their use is recommended but not required.

Study Categories:

- 1. For investigational studies involving drug or devices, all sections of this application need to be completed. Use consent template 1.
- 2. For Full Board social or behavioral research, sections: 1, 2, 3, 4, 5.0-5.3, 6, 7, 8, 9, 10, 11, and 13 need to be completed. Use consent template 2.
- 3. For establishment of a research registry, sections: 1, 2, 3, 4, 5.0-5.3, 6, 7, 8, 9, 10 and 13 need to be completed. Use consent template 3.

SECT	ION 1 - BASIC STUDY INFO	PRMATION		
1.0	Type of Submission:	X INITIAL APPLICATION	☐ RESUBMISSION TO AD	DRESS CONTINGENCIES
1.1	Name of Principal Inve	estigator for IRB Proposal	: [name]	
1.2		Project location: AMERICA CENTER	X SAINT FRANCIS CAMPUS	☐ BURGDORF CLINIC/BANK OF
		☐ MOUNT SINAI CAMPUS ☐ OTHER (PLEASE SPECIF	☐ ASYLUM HILL FAMIL FY):	Y MEDICINE
1.3	Type of review reques	ted: X FULL BOARD		
1.5	Complete Associated	stoperative Analgesia after	пір Аплгоscopy.	
1.6	Name of PI on the gra	nt: N/A		
1.7			ocal Infiltration Analgesia fo	r Hip Arthroscopy
1.8	Identify any external f	unding source for this stu	ıdy: N/A	
1.9 Anes		unding source for this stu lospital and Medical Center	dy (e.g. Academic Affairs, dept. fund , Hartford, CT.	ds etc.): Department of
1.10	Identify the sponsor f	or this study (e.g. PI, ECOG,	Pfizer, etc): N/A	
1.11	-		est or other relationship witl by each investigator and submitted v	
1.12	Will the PI benefit per	sonally from this study?	☐ YES X NO	
1.13	Will the sponsor inde	mnify subjects in the ever	nt of a research-related injui	ry? YES X No

	If yes, proceed to	`	A second death of		(1	A DESCRIPTION OF A	laran (a)
.1 If collaborating that describes t	with other sites	s, provide the na	ame of each	Institution, and	place an x u	nger the co	iumn(s)
obtained IRB ap				. Flovide the di	ite that the c	ther motitud	
				EEG (1 100
Institution's Name	Recruitment		Interactions (e.g. survey)	Interventions (e.g. needle stick)	Follow-up	Analysis	IRB Approva
32 L	-	Subjects	(e.g. survey)	(e.g. fieedle stick)		631 111	Date
	A	The Webser 2	Sugarous ATM	- 337	- 11i - 1		
THE SHIT OF THE STREET		000 7.1 (0007)					
Additional Comme	ents:	A Magni Carl N					
.2 Indicate the e	xpected percer	tage of enrollm	ent at each	applicable site,	and place ar	X in the ap	propriate
cell to indicat	e which institu	tion, based on t	he preponde	erance of the ex	pected enrol	lment, you a	are
requesting se applicable site		of record or tha	it independe	nt IRB approval	will be soug	Int from eac	n
applicable sic							
Institution's Nar	ne % to be Ei	rolled/Consented	d Reques	ted IRB of Record	Indepe	ndent IRB Re	view
SFHMC							1 5 8
						- J	
nformation on mul	ti-center trials	di mu					
		f no, skip to section	n 4 if wee proc	eed to 3.4)	YES X No	X I	
.5 is this a much	-center than (no, akip to acciroi	11 4, 11 yea proc	200 10 0.47	TEO X NO		
.4 Will SFHMC s	erve as the lea	d institution?	□ YES C) No	1 -1 4	m S ₁	
.5 Describe the	plans for comp	nunication amo	na sites in to	erms of protoco	l modificatio	ns. unantic	ipated
	interim result						
SECTION 4 - PROJECT	T CHARACTERIST	ICS, SUMMARY AN	ID DESIGN				
		frame during w		dy will be cond	ucted:		
	t Date (mm/dd/vv	v):	Exi	pected Complet	ion Date (mm	/dd/yyyy):	
Expected Start Date (mm/dd/yyyy): Expected Completion Date (mm/dd/yyyy):							

	4	hant describe t	constants to a co	neor apetrointes	inal
Provide the general therap pancreatic or psychiatry, addictive to	eutic area and sub-area(s) that behaviors, gambling).	best describe y	our study (e.g., ca	ancer, gastronites	urran,
Primary Area	Sub- Area		2 ^{na} Sub- Area		
Ambulatory Surgery	Recovery Room				-
Place an X after the applic	able study phase:				
Phase I Phase II		/ (Post Marketing) X Not a c	linical trial	
Fliase I I liase II I	That in this en	19 (10 c) = 10 19			
For post-marketing trials.	describe any post-marketing re	equirements im	posed on the use	e of this drug	by
the FDA. NONE	Joseph Market Ma		T - 18		
the FDA. NONE					
				23 . 3	_
Diena on V affor all charac	teristics that are applicable to	the study desig	n:		
Place all A alter all Charac	teristics that are applicable to			N. Daniel State	_
Pilot Study	Case-Control	Rand	omization	X	
I not otday	Study				
		Place	ha		
Observational Study	Double-blind				\dashv
Cross-Sectional	Chart review	Norm	al Controls	HIII S	
Study					
	Focus Group		and the second		
Survey	The second secon				
Other (specify): Observer E	linded				
			No. of the Land		211
		35 IS I D			
			O 1 1 1 1 1 1 1 1 1 1 1 1 1 1 1 1 1 1 1		
	1 - 11. In a service of the least	orma Ma hava	proviously shown	that injecting I	oca
Provide 2 or 3 sentences	describing your project in lay t	erms, we have	previously shown	that injuding i	24
sthetic solution around the hip	joint under ultrasound guidance	prior to start of s	surgery will decrea	ase the pain ai	IU
a-medication requirements after	er surgery. This study is being un	idertaken to com	pare the pain con	troi using eitne	? Γ
income versus linesemal but	pivacaine. Liposomal bupivacaine	can notentially	provide pain relief	lasting up to	72
Macalle Actana irbosomai put	tale sein telief up to 12 h	our potentially			
	an provide pain relief up to 12 no	Juis.			
rs while regular bupivacaine o			100		
irs while regular bupivacaine o	diam of their numbers (D	4.7. 4.9 and 4.0 com	blood should not exce	ed the equivalent	of f
		4.7, 4.0 and 4.9 com	Direct attend not exec		
Provide a summary descrip	tion of this project. (Responses				
	ition of this project. (Responses			attended and tenditions	tion
Provide a summary descrip		is to compare the	officacy and due	etian at inflitra	
Provide a summary descrip	lims: The objective of this study	is to compare the	e efficacy and dur	ation of inflitra	or I
Provide a summary descript pages) ypotheses, Objectives and A	Nims: The objective of this study	ne. By using long	acting liposomal	bupivacaine r	DT L
Provide a summary descript pages) ypotheses, Objectives and A		ne. By using long	acting liposomal	bupivacaine r	DT L

Patients undergoing hip arthroscopy experience moderate to severe postoperative pain. Effective pain control after surgery is an important component in the overall management of these patients. Good pain control encourages early participation in rehabilitation program, increases success of the surgery, and improves patient satisfaction. Typically, postoperative analgesia is provided to these patients either with nerve blocks (psoas compartment lumbar plexus block and sciatic nerve block) or opioid medications (1,2,3). Both these methods provide good pain relief but nerve blocks are associated with weakness of lower extremity muscles which interferes with early ambulation and increase the risk of falls while narcotic medications increase the risk of nausea, vomiting, itching, constipation, ileus, urinary retention,

sedation and respiratory depression.

Ultrasound guided peri-articular Hip infiltration with local anesthetic solution is an alternative analgesic technique that has been shown to reduce pain, opioid consumption and facilitate earlier discharge from hospital after surgery without causing any weakness of lower extremity. The typical duration of analgesia after peri-articular analgesia lasts only for 8-10 hours. When the effect of injected local anesthetic solution wears off, patients start relying on opioid pain medications for pain control. By using long acting liposomal bupivacaine for LIA we hypothesized that we will provide prolonged duration of analgesia and significantly reduce pain tablet consumption.

Liposomal bupivacaine has the same active ingredients as bupivacaine. Both act to block the generation and conduction of nerve impulses associated with pain. Liposomal bupivacaine consists of bupivacaine encapsulated within

a hydrophobic lipid membrane. The lipid membrane forms numerous capsules of the drug that are independent of each other (liposomes). Bupivacaine is released from the multivesicular liposomes over a prolonged period of time. (4)

- Lumber Plexus Blockade Reduces Pain After Hip Arthroscopy: A Prospective Randomized Controlled Trial. YaDeau J, Tedore T, Goytizolo E, Kim D, Green D, Westrick A, Fan R, Rade M, Ranawat A, Coleman S, Kelly B. Anesthesiology & Analgesia 2012; 115(4): 968-972.
- 2. The analgesic impact of preoperative lumbar plexus blocks for hip arthroscopy. A retrospective review. Schroeder K, Donnelly M, Anderson B, Ford M, Keene J. Hip International 2013; 23(1): 93-8.
- Are Femoral Nerve Blocks Effective for Early Postoperative Pain Management After Hip Arthroscopy? Ward J, Albert D, Altman R, Goldstein R, Cuff G, Youm T. Arthroscopy: The Journal of Arthroscopic and Related Surgery 2012; 28(8): 1064-69.
- 4. Liposomal bupivacaine: A long-acting anesthetic for postsurgical analgesia. Formulary 2012.

Preliminary Studies:

Please attach a copy of the full protocol if available.

- 4.7 Provide an outline of the experimental design addressing the following: time line of the study from initiation through data analysis, procedures including a time sequence of when those procedures that involve human subjects will be performed and how they will be monitored.
 - 1. Preoperative evaluation and consent
 - 2. General anesthesia for hip arthroscopy
